5.1.2 Treatment Regimen

A clinical care nurse will provide instruction to participants allocated to the Jacki arm on safe and appropriate use of the Jacki (for example, how to put on the jacket and tuck drainage tubes into jacket pockets, and the need to remove drainage tubes from jacket pockets prior to removing the jacket). Participants in the Jacki arm will be encouraged to use the jacket at home between discharge and their follow-up clinic appointment; no minimum amount of use is required.

Participants in both groups will receive all usual pain management including prescription of pain medications and instructions on pain management post-discharge as standard of care.

The treatment period for participants in both arms is from discharge from the hospital post mastectomy until the follow-up clinic appointment at which all drains are removed, usually in 7-14 days, sometimes as long as 28 or (rarely) 42 days.

5.1.3 Instruments Measuring Study Outcomes

Participants will complete study questionnaires self-reporting pain, pain management, breast symptoms and health related quality of life at three time points (see section 10, Study Calendar). Questionnaires will be answered using pen and paper in the hospital on the first (or second) day post-surgery (T1), at home (T2), or in follow-up clinic after all drains are removed (T3). If participants cannot answer the T3 questionnaire in clinic, a research coordinator will contact the participant to administer the questionnaire within 24 hours of the follow-up appointment via telephone interview or secure file exchange (using the Partners Biscom Delivery Server). Instruments are the following:

Demographic questionnaire (T1)

The questionnaire includes age, language spoken at home, ethnicity, race, marital status, education, and occupational status.

Pain Intensity Numeric Scale (PINS) (T1, T2, T3)

The PINS measures pain intensity with a single item, on a 0-10 scale and is in common clinical use.

Pain Frequency and Pain Intensity Distress (Symptom Distress Scale) (T1, T3)

Two items from the Symptom Distress Scale^{25,26} measure pain frequency and pain intensity in the past week, on a 5-point scale.

Patient-Reported Outcomes Measurement Information System (PROMIS®) Pain Intensity (T1, T3)

This 3-item instrument from the PROMIS item bank²⁷ measures pain intensity over the past week and right now, on a 5-point scale (PROMIS Item Bank v.1.0 – Pain Intensity – Short Form 3a).

Patient-Reported Outcomes Measurement Information System (PROMIS®) Pain Interference (T3)

This 8-item instrument from the PROMIS item bank²⁷ measures the interference of pain with daily activities and social relations, on a 5-point scale (PROMIS Item Bank v.1.0 – Pain Interference – Short Form 8a).

Pain Management (T2)

Participants will keep a daily pain diary between hospital discharge and follow-up clinic appointment (the T2 period) to document pain intensity, use of pain medications, and whether and how long they wear post mastectomy garments each day.

EORTC QLC-C30 (T3)

The EORTC QLQ- C30²⁸ is a 30-item questionnaire with 5 functional subscales, global health status quality of life subscale, and 9 symptom subscales/items. The time it takes to complete the questionnaire is approximately 11 minutes. The C30 has been used in over 3000 clinical trials and in 81 languages.²⁹ Authors of a recent meta-analysis³⁰ of the C30 performance concluded that all subscales perform reliably except cognitive function, a 2-item subscale assessing memory and concentration. Raw scores for the QLQ-C30 range from 0 to 100 and can be transformed and compared to reference values published in the EORTC QLQ-C30 manual.

EORTC QLQ-BR23 (T3)

The QLQ-BR23 supplementary Breast Cancer Module is comprised of 23 questions in five multi-item scales to assess side effects of surgery, arm and breast symptoms, body image, sexual functioning and future perspective. Cronbach's alpha coefficient results for QLQ-BR23 have been reported at 0.873.²⁹

Medical Record Review (T1 and T3)

A member of the study team will record clinical data, such as cancer diagnosis (if any) and surgery details at T1 prior to the participant's hospital discharge, and documentation from the medical record of pain and pain management post-discharge within 1 week after the T3 visit.

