7. ADVERSE EVENTS: LIST AND REPORTING REQUIREMENTS

7.1 Adverse Events

7.1.1.1 Adverse Event List for the Jacki Recovery Jacket

The Jacki has not previously been studied, and no adverse events or serious adverse events have been reported to A Little Easier Recovery® or at the enrolling study sites, which have previously provided jackets to some post-operative patients.

Potential adverse events include the following:

- 1.) A participant wearing the jacket may remove the jacket without first removing the drains from the pockets. This may cause pain and/or the drains to be dislodged, which would require a trip to the hospital to have them re-inserted. It could also lead to a greater risk of infection at the site of the drains.
- 2.) A participant wearing the jacket may become too warm in warm weather or may develop a skin reaction to the jacket, which is made of 50% cotton and 50% polyester.

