10. STUDY CALENDAR

Measure	Inpatient Post Mastectomy (T1)	At Home Post-Discharge (T2)	Follow-up Clinic Appointment (T3)
Participant Demographics	X		
Pain Intensity Numeric Scale (0-10)	X	X	X
Pain Frequency and Intensity Symptom Distress Scores	X		X
Health Related Quality of Life			X
Breast Symptoms			X
Pain Management		X	
Post-Discharge Pain, Pain Management, Complications (Documented in Electronic Medical Record)			X
Participant Clinical Characteristics (Diagnosis, Treatment Regimen)			

Documented in the Medical Record)			
-----------------------------------	--	--	--

T1: First (or second) day post mastectomy, during inpatient stay
T2: Exclusive of day discharged and day of follow-up when all drains are removed, daily for 7-42 days
T3: Day of follow-up clinic appointment when all drains are removed

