12.1.2 Responsibility for Data Submission

Investigative sites within DF/HCC or DF/PCC are responsible for submitting data and/or data forms to the Dana-Farber research study team according to the schedule set by the Dana-Farber research study team. All data will be submitted within 10 days of the participant's T3 appointment.

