Very poor						Excellent

Patients sometimes report that they have the following symptoms or problems. Please indicate the extent to which you have experienced these symptoms or problems during the past week.

During the past week:	Not at All	A Little	Quite a Bit	Very Much
31. Did you have a dry mouth?	1	2	3	4
32. Did food and drink taste different than usual?	1	2	3	4
33. Were your eyes painful, irritated or watery?	1	2	3	4
34. Have you lost any hair?	1	2	3	4
35. Answer this question only if you had any hair loss: Were you upset by the loss of your hair?	1	2	3	4
36. Did you feel ill or unwell?	1	2	3	4
37. Did you have hot flushes?	1	2	3	4
38. Did you have headaches?	1	2	3	4
39. Have you felt physically less attractive as a result of your disease or treatment?	1	2	3	4
40. Have you been feeling less feminine as a result of your disease or treatment?	1	2	3	4
41. Did you find it difficult to look at yourself naked?	1	2	3	4
42. Have you been dissatisfied with your body?	1	2	3	4
43. Were you worried about your health in the future?	1	2	3	4
During the past four weeks:	Not at All	A Little	Quite a Bit	Very Much
44. To what extent were you interested in sex?	1	2	3	4
45. To what extent were you sexually active? (with or without intercourse)	1	2	3	4
46. Answer this question only if you have been sexually active: To what extent was sex enjoyable for you?	1	2	3	4

During the past week:	Not at All	A Little	Quite a Bit	Very Much
47. Did you have any pain in your arm or shoulder?	1	2	3	4
48. Did you have a swollen arm or hand?	1	2	3	4
49. Was it difficult to raise your arm or to move it sideways?	1	2	3	4
50. Have you had any pain in the area of your affected breast?	1	2	3	4
51. Was the area of your affected breast swollen?	1	2	3	4
52. Was the area of your affected breast oversensitive?	1	2	3	4
53. Have you had skin problems on or in the area of your affected breast (e.g., itchy, dry, flaky)?	1	2	3	4

Reduction of Post Mastectomy Pain with the Jacki® Recovery Jacket: Randomized Trial

QUESTIONNAIRE 2

Thank you

Thank you in advance for filling out this daily diary questionnaire, which asks about your pain, medications for pain, and clothing you wear each day at home after your surgery until you return for your follow-up appointment. Please answer the daily diary questionnaire **at the end of each day**.

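### Section 5.1.3 and the study calendar disagree on whether the T3 record review covers complications, and no questionnaire directly asks about drain dislodgement, drain-site infection or garment overheating

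*Combined protocol and SAP*

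**What the plan says.** Two places define the post-discharge record review. Section 5.1.3, under Medical Record Review, describes it as "documentation from the medical record of pain and pain management post-discharge within 1 week after the T3 visit". The study calendar in section 10 has a row marked at T3 that reads "Post-Discharge Pain, Pain Management, Complications (Documented in Electronic Medical Record". Complications appear in the second and not in the first.

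Section 7.1.1.1 lists what the jacket might do. If it is taken off with the drains still in the pockets, "This may cause pain and/or the drains to be dislodged, which would require a trip to the hospital to have them re-inserted". The list continues: "It could also lead to a greater risk of infection at the site of the drains". It adds that the wearer "may become too warm in warm weather or may develop a skin reaction to the jacket". The same section states that the garment has not been studied before.

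The participant instruments are in Appendix A. The introduction to the daily diary (Questionnaire 2) says that it "asks about your pain, medications for pain, and clothing you wear each day at home". Questionnaire 3, at T3, contains the pain items, the QLQ-C30 and the QLQ-BR23, with one free-text line confined to pain and pain relief.

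Section 7.3 requires investigators to report any adverse event on study to the Overall PI within 24 hours. Section 7.4 requires all of them on the clinical data forms. Neither describes how participants are to be questioned.

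**The concern.** The point concerns how harms are collected, not how they are analysed. A member of staff who works from 5.1.3 and one who works from the calendar would abstract different things from the same record. The difference falls on the events most likely to leave a trace there: a drain that came out and had to be replaced, and an infection at the drain site.

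These events arise at home, between discharge and the visit at which all drains are removed. The participant is the natural source, yet the instruments hardly ask her. The contact after discharge described in 5.1.1 is a reminder to fill in the diary, not a check for problems.

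No blinding is described, and a visible garment cannot be hidden from its wearer. That the comparison is open-label is an inference from the design. In such a comparison, harms that are collected only when someone volunteers them are hard to interpret, whether counts are low or differ between arms.

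**Working it through.** No figure of the plan is in dispute, so the check sets each named harm against each place where it could be recorded. The harms come from 7.1.1.1, the items from Appendix A, and the two record-review scopes from 5.1.3 and section 10.

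| Named harm | Diary (T2) | Questionnaire 3 (T3) | Record review as in 5.1.3 | Record review as in the calendar |
|---|---|---|---|---|
| Pain | Daily 0-10 score | 0-10 score and further pain items | Yes | Yes |
| Drain dislodged, with re-insertion | None | None | Not mentioned | Probably, as a complication |
| Drain-site infection | None | None direct | Not mentioned | Probably, if treated |
| Too warm in the jacket | None | None | Not mentioned | Unlikely to be in the record |
| Skin reaction to the jacket | None | Item 53, in part | Not mentioned | Only if noted clinically |

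Notes on the T3 column:

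- Item 53 asks both arms about skin problems in the area of the affected breast. Questionnaire 3 tells women to read its past-week questions as the time since leaving hospital, so the item is directed at the home period. It is limited to the breast area and not tied to any garment.
- Item 37 asks about hot flushes, which does not measure overheating from clothing.
- Items 50 to 52 ask about pain, swelling and sensitivity of the breast area. They could overlap with an infection but cannot identify one.

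Count of direct patient-reported coverage: pain is 1 of 5, skin reaction is a partial 1 of 5, and dislodgement, drain-site infection and overheating are 3 of 5 with no direct item (1 + 1 + 3 = 5).

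Count for the record review: the 5.1.3 wording names 1 of 5 (pain). The calendar wording would probably reach 3 of 5 (pain, dislodgement, treated infection). The gap between the two readings is therefore two harms, and they are the two drain complications.

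Burden of asking directly, with three separate yes/no items: the calendar has the diary running daily for 7 to 42 days, so diary items would mean 3 × 7 = 21 to 3 × 42 = 126 answers per woman. Asked once at T3, they mean 3.

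**The case against.** The strongest reply is that reporting does not depend on 5.1.3. Sections 7.3 and 7.4 bind investigators to report every adverse event, in both arms, on the clinical data forms. Section 5.1.3 describes outcome instruments, does not say that the review is confined to pain, and refers to the calendar, where complications are marked. By the protocol's own account a dislodged drain means a hospital trip, so a record of it is likely. T3 is the visit at which all drains are removed, so a missing drain should be noticed. The clinical data form is not reproduced and may already have a complications field.

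Most of this stands, and it limits the point. A reader might infer that a site following 5.1.3 would fail to record a dislodged drain or an infection. The documents do not support that, because the reporting duty applies whatever 5.1.3 says. What the reply leaves untouched is that a duty to report is not a method of finding out, and that two descriptions of one review differ.

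A reader might also infer that reports will be unequal because the nurse teaches only jacket participants about the pocket hazard (5.1.2). The documents do not describe what drain teaching usual-care women receive, so the inference is unsupported. Nor can anyone calculate how far a zero count would understate risk, since the documents give neither harm rates nor the fraction of events that would be captured.

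Finally, a reader might object that the review can be done as early as the T3 day. The wording allows up to a week, and by T3 the drains are out and the treatment period is over. A later fixed window would be a preference, not a correction.

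**Conclusion.** The point holds as an inconsistency to be reconciled and a gap in solicited collection. Two of the five named harms, drain dislodgement and drain-site infection, fall inside or outside the record review depending on which section staff follow. Three of the five have no direct participant item in either arm. If 5.1.3 is followed, those three depend on unsolicited reporting. If the calendar is followed, overheating and mild skin reactions would still probably be missed by the record review.

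This rests on three assumptions: that the comparison is open-label, that the clinical data form does not already resolve the conflict, and that no questioning about adverse events takes place beyond what is written. The primary pain comparison is not affected. The change is worth making because it is cheap and because harm data on a previously unstudied garment should not depend on which section a member of staff reads.

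**What to change.** 1. In 5.1.3, add complications to the post-discharge record review so that it matches section 10. Name the events to be abstracted: drain dislodgement, drain re-insertion, drain-site infection and skin reaction. Put identical fields for them on the clinical data form in both arms. The timing can stay as written; a review within one week of T3 already fits the rule that "All data will be submitted within 10 days of the participant's T3 appointment".
2. Add three separate yes/no items, worded identically for both arms: whether a drain was pulled or came out, whether a garment irritated the skin, and whether the participant was too warm in a garment. Referring to any garment keeps the items answerable in usual care, since the diary already lists mastectomy bras and camisoles. Asking once, in Questionnaire 3, avoids adding to the daily diary.

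The cost is a few form fields and three short questions per participant, with no extra visits or staff. One limit remains: women without a T3 questionnaire would not answer the new items. At the projected attrition that is 149 − 130 = 19 participants, for whom adverse event reporting and any available record would still be the only sources.

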5.2 Pre-Treatment Criteria

Not applicable.

5.3 Agent Administration

Not applicable.

5.4 Definition of Dose-Limiting Toxicity (DLT)

Not applicable.

5.5 General Concomitant Medication and Supportive Care Guidelines

Not applicable.

5.6 Criteria for Taking a Participant Off Protocol Therapy

Not applicable.

5.7 Duration of Follow Up

Not applicable.

5.8 Criteria for Taking a Participant Off Study

Participants will be removed from study when any of the following criteria apply:

- Lost to follow-up
- Withdrawal of consent for data submission
- Death
- It is considered to be in the participant's best interest
- The study device or procedures are found to be unsafe or ineffective
- There is any problem with using the study device or following study procedures
- The participant's condition worsens
- A decision is made to close the study
- Or for any other unforeseen reasons that make it necessary to stop the participant's participation in the research study

The reason for taking a participant off study, and the date the participant was removed, must be documented in the case report form (CRF).

For Centralized Subject Registrations, the research team submits a completed Off Treatment/Off Study form to ODQ when a participant comes off study. This form can be found on the ODQ website or obtained from the ODQ registration staff.

6. DOSING DELAYS/DOSE MODIFICATIONS

Not applicable.

7. ADVERSE EVENTS: LIST AND REPORTING REQUIREMENTS

7.1 Adverse Events

7.1.1.1 Adverse Event List for the Jacki Recovery Jacket

The Jacki has not previously been studied, and no adverse events or serious adverse events have been reported to A Little Easier Recovery® or at the enrolling study sites, which have previously provided jackets to some post-operative patients.

Potential adverse events include the following:

- 1.) A participant wearing the jacket may remove the jacket without first removing the drains from the pockets. This may cause pain and/or the drains to be dislodged, which would require a trip to the hospital to have them re-inserted. It could also lead to a greater risk of infection at the site of the drains.
- 2.) A participant wearing the jacket may become too warm in warm weather or may develop a skin reaction to the jacket, which is made of 50% cotton and 50% polyester.

7.2 Adverse Event Characteristics

Adverse events are not graded.

7.3 Expedited Adverse Event Reporting

7.3.1 Investigators **must** report to the Overall PI any adverse event that occurs while the subject is on study. The event must be reported to the Overall PI within 24 hours.

7.4 Routine Adverse Event Reporting

All Adverse Events **must** be reported in routine study data submissions to the Overall PI on the clinical data forms. **AEs reported through expedited processes must also be reported in routine study data submissions.**

8. PHARMACEUTICAL AND/OR IMAGING AGENT INFORMATION

Not applicable.

9. BIOMARKER, CORRELATIVE, AND SPECIAL STUDIES

Not applicable.

10. STUDY CALENDAR

Measure	Inpatient Post Mastectomy (T1)	At Home Post-Discharge (T2)	Follow-up Clinic Appointment (T3)
Participant Demographics	X		
Pain Intensity Numeric Scale (0-10)	X	X	X
Pain Frequency and Intensity Symptom Distress Scores	X		X
Health Related Quality of Life			X
Breast Symptoms			X
Pain Management		X	
Post-Discharge Pain, Pain Management, Complications (Documented in Electronic Medical Record)			X
Participant Clinical Characteristics (Diagnosis, Treatment Regimen)			

Documented in the Medical Record)			
-----------------------------------	--	--	--

T1: First (or second) day post mastectomy, during inpatient stay
T2: Exclusive of day discharged and day of follow-up when all drains are removed, daily for 7-42 days
T3: Day of follow-up clinic appointment when all drains are removed

11. MEASUREMENT OF EFFECT

11.1 Antitumor Effect – Solid Tumors

Not applicable.

11.2 Antitumor Effect – Hematologic Tumors

Not applicable.

11.3 Other Response Parameters

Other endpoints include pain, breast cancer symptoms, and health related quality of life and are measured as described in section 5.

12. DATA REPORTING / REGULATORY REQUIREMENTS

Adverse event lists, guidelines, and instructions for AE reporting can be found in Section 7.0 (Adverse Events: List and Reporting Requirements).

12.1 Data Reporting

12.1.1 Method

The Dana-Farber research study team will collect, manage, and perform quality checks on the data for this study.

12.1.2 Responsibility for Data Submission

Investigative sites within DF/HCC or DF/PCC are responsible for submitting data and/or data forms to the Dana-Farber research study team according to the schedule set by the Dana-Farber research study team. All data will be submitted within 10 days of the participant's T3 appointment.

12.2 Data Safety Monitoring

The PI will monitor the study, including review of study conduct, enrollment, adverse events with prompt reporting of AEs and other study-related information to the IRB, sponsor, and other agencies as appropriate. Good Clinical Practice (GCP) will be followed for conduct of the study and modifications; deviations will be reported to the IRB, along with an annual status report as per IRB guidelines.

12.3 Multicenter Guidelines

Not applicable.

12.4 Collaborative Agreements Language

Not applicable.

13. STATISTICAL CONSIDERATIONS

13.1 Study Design/Endpoints

The study is a randomized trial of the Jacki recover jacket versus usual care for post-discharge pain management in patients who received mastectomy with reconstructive surgery in one or both breasts. All participants will complete questionnaires measuring pain, pain management, breast symptoms, and health-related quality of life (Appendix A). Questionnaires will be completed at three time points: pre-discharge (T1), at home over approximately 7-14 (up to 42) days (T2), and at follow-up clinic when all drains are removed (T3). Participants will receive usual pain management or the Jacki plus usual pain management post-discharge. Clinical data will be collected by a member of the research study team using a clinical data form.

13.2 Sample Size, Accrual Rate and Study Duration

The primary objective of this study will be to compare pain intensity (measured on the 0-10 scale, PINS) at the follow-up clinic appointment when all drains are removed (T3) between those randomized to UC or Jacki groups. A reduction of 1.0 on the PINS is thought to be clinically significant. With a sample size of 130 there is 80% power to detect a 1-point difference in PINS between UC and Jacki groups using a Wilcoxon rank sum test at the 2-sided 0.1 significance level assuming a standard deviation of 2.2 from

the preliminary study. The following table depicts the impact on power if the standard deviation at the follow-up visits is smaller or larger than estimated.

Standard Deviation	Power
1.8	91%
2.0	86%
2.2	80%
2.4	74%
2.6	68%

With a projected 13% rate of attrition, a total of 149 participants enrolled will yield an analytic sample of 130 evaluable participants. This number of participants will be accrued and will complete data collection within 10 months, based on clinical volume .

Accrual Targets				
Ethnic Category	Sex/Gender			
	Females	Males	Total	
Hispanic or Latino	39	+ 0	=	39
Not Hispanic or Latino	91	+ 0	=	91
Ethnic Category: Total of all subjects	130	+ 0	=	130
Racial Category				
American Indian or Alaskan Native	0	+ 0	=	0
Asian	6	+ 0	=	6
Black or African American	13	+ 0	=	13
Native Hawaiian or other Pacific Islander	0	+ 0	=	0
White	111	+ 0	=	111
Racial Category: Total of all subjects	130	+ 0	=	130

No interim analyses are planned due to the short duration, minimal risk, and minimal burden of the study. There are no early stopping rules.

